8.9.2 Analysis

Biomarker data will be analyzed using the FAS and data up to the EOS visit.

For biomarkers standard summary statistics for absolute values, absolute change and percent change from baseline will be presented, by visit and treatment group.

Summary statistics of percentage changes will be derived from the geometric mean of the ratio to baseline. Because geometric mean of data is equivalent to $\exp(\text{mean of log-transformed data})$, the geometric mean of the ratio to baseline is equivalent to $\exp(\text{mean of } (\log[\text{post-baseline}] - \log[\text{baseline}]))$. Geometric mean of the ratio to baseline will be transformed into a percentage change by using the transformation $x \rightarrow ((x-1) \times 100)$.

The CV of the geometric mean will be derived as:

$$100 \times \sqrt{\exp\left((SD_{\log})^2\right) - 1}$$

Note that anti-cardiolipin antibodies are only collected at baseline and therefore only the baseline summaries will be presented for this parameter.

Biomarkers will be listed using the FAS.

9 GENERAL STATISTICAL METHODOLOGY

9.1 General rules for data presentations

Unless otherwise specified, data will be summarized using appropriate descriptive statistics:

- For continuous variables: number of non-missing observations, mean, standard deviation, minimum, first quartile, median, third quartile and maximum.

Results will be displayed in the format of the eCRF for median, percentiles, minimum and maximum values. They will be displayed with one additional digit for the mean and the 95% CIs. The standard deviation will be displayed with one more digit than the mean.

- For dichotomous or categorical variables: number of non-missing observations, and frequency with percentage per category. Denominators for percentages are the number of subjects in the pertinent analysis set and treatment group, unless otherwise specified.

- For time-to-event variables: number of events, number at risk, number of censored observations and Kaplan-Meier estimates of the survival function.

In listings, subject number is presented as “SUBJID/SEX/AGE”.

A percentage change from baseline is defined as the absolute change from baseline divided by the baseline value (if the baseline value is > 0) and then multiplied by 100. In the event of baseline and post-baseline value both equal to 0, the ratio to baseline will be set to 1 (i.e., the percent change from baseline will be set to 0%). If baseline is equal to 0 and post-baseline value greater than 0 (infinite ratio) or if baseline greater than 0 and post-baseline equal to 0 ($\log[\text{ratio}] = \text{minus infinity}$), the percent change will be missing.

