3.2 Secondary objectives

The secondary objectives of the study are to evaluate the following over 6 months in adult subjects with moderate to severe SLE concurrently receiving background therapy:

- The safety and tolerability of cenerimod treatment.
- The effect of cenerimod treatment on QoL and fatigue using relevant PRO instruments.
- The effect of cenerimod treatment on SLE biomarkers.

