8.9.1 Variables

The absolute change and percent change from baseline in biomarker parameters at each post-baseline analysis visit up to EOS is calculated as follows:

- Change in biomarker parameters = Biomarker value at Visit X – Biomarker value at baseline

- Percent change in biomarker parameters = (Biomarker value at Visit X – Biomarker value at baseline) / Biomarker value at baseline × 100

Baseline is defined as the last valid biomarker value prior to first study drug intake, by time and date.

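### SAP 9.1 sets every fall from a positive baseline to 0 to missing for a log-scale reason, which also deletes defined -100% values from laboratory percent changes

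*SAP*

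**What the plan says.** Section 9.1 of the SAP gives the general definition: "A percentage change from baseline is defined as the absolute change from baseline divided by the baseline value (if the baseline value is > 0"), multiplied by 100. It then sets three rules for zeros:

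- Both values 0: "In the event of baseline and post-baseline value both equal to 0, the ratio to baseline will be set to 1", so the percent change is 0% and the subject stays in.
- Rise from 0: "If baseline is equal to 0 and post-baseline value greater than 0 (infinite ratio"), the percent change is missing.
- Fall to 0: "if baseline greater than 0 and post-baseline equal to 0", the percent change is also missing. The reason given is that the log of the ratio is minus infinity.

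The section formulas are arithmetic. For biomarkers, 8.9.1 has "Percent change in biomarker parameters = (Biomarker value at Visit X – Biomarker value at baseline) / Biomarker value at baseline × 100". Section 8.4.2 uses the same form for hematology, blood chemistry and urinalysis.

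The summary scale differs by section. For biomarkers, 8.9.2 says "Summary statistics of percentage changes will be derived from the geometric mean of the ratio to baseline". Section 8.5.3 does the same for spirometry. Section 8.4.3 sets no geometric-mean summary for laboratory data, so the default descriptive statistics of 9.1 apply.

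**The concern.** A fall to 0 is the largest decrease that a non-negative measurement can show. Under the SAP's own definition it has a finite value, yet it is removed for a reason that belongs to a different summary scale. Where percent change is summarized arithmetically, a value is kept or dropped according to the outcome itself. If one arm has more such falls, it loses more of its largest reductions.

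Two outputs could be affected. One is the laboratory percent changes, which include leukocyte differential counts (8.4.1); SAP 6.8.3.3.1 attributes a lowering of the peripheral lymphocyte count to the compound's mode of action. The other is the biomarker summaries, which serve a stated secondary objective: "The effect of cenerimod treatment on SLE biomarkers". The SAP specifies neither a substitute for zero or below-quantification values nor a count of values lost in each direction. The number of non-missing observations will be shown, but it does not separate these exclusions from missed samples.

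**Working it through.** The plan has no figure of its own to reproduce, so the check applies its formulas directly.

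**Step 1: does the definition give a value?** For an illustrative fall from 20 to 0, the 8.4.2 and 8.9.1 formula gives (0 - 20) / 20 × 100 = -100%. Section 9.1 makes it missing. On the log scale, ln(0/20) is undefined, and keeping the zero would force the geometric mean ratio to 0, a change of -100% for the whole group. The exclusion therefore has a reason on the log scale and none on the arithmetic scale.

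**Step 2: what does dropping falls to 0 do?** From the SAP: 325 subjects in five equal arms, 325 / 5 = 65 per arm. Assumed, because the documents do not give them: k subjects fall to 0, all others have a common ratio r to baseline, and a zero is carried on the log scale as a substituted ratio s. With f = k/65:

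- Mean under 9.1: (r - 1) × 100.
- Arithmetic mean with -100% kept: [(1 - f)(r - 1) - f] × 100.
- Geometric mean change with substitution: [exp((1 - f) ln r + f ln s) - 1] × 100.

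For k = 3 and r = 0.7, the arithmetic mean is (62 × (-30) + 3 × (-100)) / 65 = -2160 / 65 = -33.2%. With s = 0.1 the geometric result is exp((62/65) ln 0.7 + (3/65) ln 0.1) - 1 = exp(-0.4465) - 1 = -36.0%.

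| r = 0.7 | Under 9.1 | Arithmetic, -100% kept | Geometric, s = 0.5 / 0.1 / 0.02 |
|---|---|---|---|
| 1 of 65 | -30.0% | -31.1% | -30.4 / -32.1 / -33.7% |
| 3 of 65 | -30.0% | -33.2% | -31.1 / -36.0 / -40.6% |
| 7 of 65 | -30.0% | -37.5% | -32.5 / -43.2 / -52.3% |
| 13 of 65 | -30.0% | -44.0% | -34.6 / -52.6 / -65.6% |

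With r = 0.9, 9.1 shows -10.0%, and the arithmetic mean with -100% kept runs from -11.4% (1 of 65) to -28.0% (13 of 65). With no zeros there is no difference.

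**Step 3: what does the whole rule do?** Rises from 0 are dropped too. On the log scale with r = 0.7, substituted ratio 0.1 for a fall and 10 for a rise, against -30.0% under 9.1:

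- 3 falls, no rises: -36.0%.
- 3 falls, 3 rises: -27.7%.
- No falls, 3 rises: -20.9%.

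The clause on falls has a fixed direction. The rule as a whole does not.

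**The case against.** The strongest defense is that the exclusion is disclosed, has a stated reason, and follows from the chosen log-scale summary. For biomarkers and spirometry some convention is unavoidable, and half a quantification limit is only one of several; the documents give no such limit. This stands, but it does not cover the laboratory percent changes, which the SAP does not put on a log scale.

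It is also fair that little information is lost overall. Absolute values and absolute changes keep these subjects, biomarkers are listed, and marked laboratory abnormalities are summarized separately (8.4.3). These summaries lie outside the testing strategy in 7.1.1. This stands too, and it keeps the point small.

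A reader might infer that the rule drops complete normalizations and that biomarker reductions are therefore understated in this trial. The documents do not support that. They nowhere equate 0 with a normal result. They do not show that any of the biomarkers summarized numerically (anti-nuclear, anti-dsDNA and anti-Smith antibodies, C3, C4) is ever reported as exactly 0. The matching exclusion of rises from 0 pulls the other way.

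**Conclusion.** Section 9.1 conflicts with its own definition and with the formulas in 8.4.2 and 8.9.1 for falls to 0. It is wrong as written only for arithmetic percent changes, in practice the laboratory ones. There a defined -100% is deleted according to outcome, which can understate reductions among subjects with baseline above 0. For the geometric-mean summaries the gap is a missing convention for zeros, not an error.

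The size is unknown. Every magnitude above rests on an assumed number of zeros (1 to 13 of 65), an assumed common ratio and, on the log scale, an assumed substitute. With 13 of 65 at zero and r = 0.7, the substitute alone moves the result from -34.6% to -65.6%, so none of these is a true value. The issue is minor and descriptive, with no effect on the primary or secondary efficacy tests.

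**What to change.** Amend SAP 9.1 in three parts:

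1. Limit the log-ratio exclusion to geometric-mean summaries (8.5.3, 8.9.2). For arithmetic percent change (laboratory, 8.4.2) keep -100%, leaving only rises from 0 undefined.
2. For geometric-mean summaries, pre-specify one positive substitute for zero or below-quantification values, for example half the quantification limit, applied at both baseline and post-baseline. Using the same substitute at both times also reproduces the present rule that 0 to 0 is a ratio of 1.
3. Report, by arm and visit, the number of values substituted or excluded in each direction.

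The cost is one derivation rule and a count in the affected tables. The downside is that the log-scale summary then depends on the chosen substitute, so that choice should be fixed before unblinding and stated with the output.

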10 INTERIM ANALYSES

No interim analyses are planned according to protocol.

12 APPENDICES

12.1 Visit and assessment schedule

PERIODS	Name	SCREENING	TREATMENT PERIOD 1							
	Duration	Up to 60 days	From Day 1 to Month 6							
VISITS	Number	1	2	2a	3	4	5	6	7	8
	Name	Screening	Randomization ⁽¹⁾		Month 1	Month 2	Month 3	Month 4	Month 5	Month 6
	Time	Day -60 to Day -1	Day 1	Day 2	Day 30 (±2 days)	Day 60 (±7 days)	Day 90 (±7 days)	Day 120 (±7 days)	Day 150 (±7 days)	Day 180 (±7 days)
Informed consent		X								
Inclusion/exclusion criteria		X	X							
Demographics		X								
Smoking and alcohol consumption status		X								
Medical history and SLE history		X								
SLE and previous/concomitant therapies		X	X		X	X	X	X	X	X
Physical examination ⁽²⁾		X	X		X	X	X	X	X	X
Body weight and height ⁽³⁾		X								
mSLEDAI-2K, BILAG, PGA, SFI		X	X		X	X	X	X	X	X
FACIT-Fatigue, PGIS-F			X				X			X
PGIC-F							X			X
SF-36v2™ and Lupus QoL			X							X
Chest X-ray ⁽⁵⁾		X								
Vital signs: SBP/DBP* ^{(6) (7)}		X	X		X	X	X	X	X	X
12-lead ECG* ⁽⁷⁾		X	X				X			X
ECG Holter* ⁽⁸⁾			X	X						
Echocardiography ⁽⁴⁾		X								X
Spirometry*		X					X			X
Ophthalmological examinations		X					X			X
OCT		X					X			

PERIODS	Name	SCREENING	TREATMENT PERIOD 1							
	Duration	Up to 60 days	From Day 1 to Month 6							
VISITS	Number	1	2	2a	3	4	5	6	7	8
	Name	Screening	Randomization ⁽¹⁾		Month 1	Month 2	Month 3	Month 4	Month 5	Month 6
	Time	Day -60 to Day -1	Day 1	Day 2	Day 30 (±2 days)	Day 60 (±7 days)	Day 90 (±7 days)	Day 120 (±7 days)	Day 150 (±7 days)	Day 180 (±7 days)
PK sampling* ⁽⁹⁾			X		X	X	X			X
Hematology and blood chemistry* ⁽¹⁰⁾		X	X		X	X	X	X	X	X
Pregnancy test ⁽¹¹⁾		X	X		X	X	X	X	X	X
Viral serology / TB test		X								
Additional sample for virology			X							
SLE biomarkers		X	X ⁽¹³⁾		X	X	X ⁽¹³⁾	X	X	X ⁽¹³⁾
Urine protein-to-creatinine ratio		X	X		X	X	X	X	X	X
Urinalysis (dipstick)		X	X		X	X	X	X	X	X
Study treatment dispensing/return and accountability			X		X	X	X	X	X	X
AEs ⁽¹²⁾ / SAEs ⁽¹²⁾		X	X		X	X	X	X	X	X

PERIODS	Name	TREATMENT PERIOD 2					
	Duration	From Month 6 up to Month 12					
VISITS	Number	9	10	11	12	13	14
	Name	Month 7	Month 8	Month 9	Month 10	Month 11	Month 12 / End-of-Treatment (EOT) / premature discontinuation of study treatment (pEOT) ⁽¹⁴⁾
	Time	Day 210 (±7 days)	Day 240 (±7 days)	Day 270 (±7 days)	Day 300 (±7 days)	Day 330 (±7 days)	
SLE and previous/concomitant therapies		X	X	X	X	X	X
Physical examination ⁽²⁾		X	X	X	X	X	X
Body weight ⁽³⁾							X
mSLEDAI-2K, BILAG, PGA, SFI		X	X	X	X	X	X
FACIT-Fatigue, PGIS-F, PGIC-F, SF-36v2 TM and Lupus QoL				X			X
Echocardiography ⁽⁴⁾							X
Vital signs: SBP/DBP* ^{(6) (7)}		X	X	X	X	X	X
12-lead ECG* ⁽⁷⁾				X			X
Spirometry*				X			X
Ophthalmological examinations							X
OCT							X
Hematology and blood chemistry* ⁽¹⁰⁾		X	X	X	X	X	X
Pregnancy test ⁽¹¹⁾		X	X	X	X	X	X
Urinalysis (dipstick)		X	X	X	X	X	X
SLE biomarkers		X	X	X	X	X	X ⁽¹³⁾
Urine protein-to-creatinine ratio		X	X	X	X	X	X
PK sampling*							X ⁽⁹⁾
Study treatment dispensing/return and accountability		X	X	X	X	X	X
AEs ⁽¹²⁾ / SAEs ⁽¹²⁾		X	X	X	X	X	X

PERIODS	Name	FOLLOW-UP					
	Duration	6 months					
VISITS	Number	15	16	17	17a	17b	18
	Name	FU1	FU2 PHONE CALL	FU3 PHONE CALL	FU3a PHONE CALL	FU3b PHONE CALL	EOS
	Time	1 month after last dose ⁽¹⁶⁾ (±7 days)	2 months after last dose ⁽¹⁶⁾ (±7 days)	3 months after last dose ⁽¹⁶⁾ (±7 days)	4 months after last dose ⁽¹⁶⁾ (±7 days)	5 months after last dose ⁽¹⁶⁾ (±7 days)	6 months after last dose ⁽¹⁶⁾ (±7 days)
SLE and concomitant therapies		X					X
Physical examination ⁽²⁾		X					X
Body weight ⁽³⁾							X
mSLEDAI-2K, BILAG, PGA, SFI		X					X
FACIT-Fatigue, PGIS-F, PGIC-F, SF-36v2™, and Lupus QoL							X
Vital signs: SBP/DBP* ⁽⁶⁾⁽⁷⁾		X					X
12-lead ECG* ⁽⁷⁾							X
ECG Holter* ⁽⁸⁾							
Echocardiography ⁽⁴⁾							
Spirometry*							X
Ophthalmological examinations							X
OCT							
PK sampling* ⁽⁹⁾							X

PERIODS	Name	FOLLOW-UP					
	Duration	6 Months					
VISITS	Number	15	16	17	17a	17b	18
	Name	FU1	FU2 PHONE CALL	FU3 PHONE CALL	FU3a PHONE CALL	FU3b PHONE CALL	EOS
	Time	1 month after last dose ⁽¹⁶⁾ (±7 days)	2 months after last dose ⁽¹⁶⁾ (±7 days)	3 months after last dose ⁽¹⁶⁾ (±7 days)	4 months after last dose ⁽¹⁶⁾ (±7 days)	5 months after last dose ⁽¹⁶⁾ (±7 days)	6 months after last dose ⁽¹⁶⁾ (±7 days)
Hematology and blood chemistry* ⁽¹⁰⁾		X					X
Pregnancy test ⁽¹¹⁾		X	X	X	X	X	X
Viral serology / TB test							
Urinalysis (dipstick)		X					X
SLE biomarkers		X					X
Urine protein-to-creatinine ratio		X					X
Study treatment dispensing/return and accountability							
AEs ⁽¹²⁾ / SAEs ⁽¹²⁾		X	X	X	X	X	X

PERIODS	Name	UNSCHEDULED		
	Duration	NA		
VISITS	Number	U1, U2, ...	I1	I2
	Name	Unscheduled ⁽¹⁵⁾	Re-initiation	
	Time	Any day between Day 1 and EOS (assessments to be performed as applicable)	Re-initiating study drug after interruption lasting more than 7 days between Day 1 and Day 14	
SLE and concomitant therapies		X	X	
Physical examination ⁽²⁾		X	X	
Body weight ⁽³⁾		X		
mSLEDAI-2K, BILAG, PGA, SFI		X		
FACIT-Fatigue, PGIS-F, PGIC-F, SF-36v2™, and Lupus QoL		X		
Chest X-ray ⁽⁵⁾		X		
Vital signs: SBP/DBP* ^{(6) (7)}		X	X	
12-lead ECG* ⁽⁷⁾		X	X	
ECG Holter* ⁽⁸⁾			X	X
Echocardiography ⁽⁴⁾		X		
Spirometry*		X		
Ophthalmological examinations		X		
OCT		X		
PK sampling* ⁽⁹⁾			X	

PERIODS	Name	UNSCHEDULED		
	Duration	NA		
VISITS	Number	U1, U2, ...	I1	I2
	Name	Unscheduled ⁽¹⁵⁾	Re-initiation	
	Time	Any day between Day 1 and EOS (assessments to be performed as applicable)	Re-initiating study drug after interruption lasting more than 7 days between Day 1 and Day 14	
Hematology and blood chemistry* ⁽¹⁰⁾		X		
Pregnancy test ⁽¹¹⁾		X		
Viral serology / TB test		X		
Urinalysis (dipstick)		X		
SLE biomarkers		X		
Urine protein-to-creatinine ratio		X		
Study treatment dispensing/return and accountability			X	
AEs ⁽¹²⁾ / SAEs ⁽¹²⁾		X	X	

One month is considered to be 30 days.

Day 1 (date of Randomization visit) is to be used as the reference date for the purpose of calculating the subsequent visit dates (and time windows).

For WOCBP, the serum pregnancy test at Visit 1 must be performed at least 3 weeks before the urine pregnancy test performed at Visit 2 prior to Randomization.

* Study treatment should not be taken before the assessment (i.e., SBP/DBP, ECGs, spirometry, laboratory tests, and PK sampling).

- (1) Prior to Randomization, the following central laboratory results must be available to confirm eligibility: ANA, anti-dsDNA, anti-HAV IgM, Hepatitis B surface antigen, Hepatitis C antibodies (anti-HCV IgG or IgM), anti-HEV IgM and/or IgG, HEV-RNA PCR (as needed), HIV1 and HIV2, varicella-zoster virus IgM antibody, urine protein-to-creatinine ratio, ALT/AST/TBIL and pregnancy test (if applicable).
- (2) A complete physical examination (i.e., inspection, percussion, palpation, and auscultation) will only be performed at Visits 1, 2, 3, 5, 8, 11, 14, and 15. For all other visits, a symptom-driven abbreviated physical examination will be performed in order to capture assessments needed for the SLEDAI-2K, the PGA, the BILAG, and the SFI.
- (3) Height only at Screening. Body weight should be measured as part of BILAG assessment at each applicable visit and recorded in the source documentation. If clinically relevant, body weight collected outside Screening, EOT and EOS visits may be reported as an Unscheduled assessment.
- (4) Echocardiography will be performed at Visit 1 (Screening) preferably within 30 days prior to Randomization for all subjects and at Visit 8 (Month 6) in approximately 175 subjects, as part of the ancillary study. In the event of premature study treatment discontinuation during TP1 (i.e., before Visit 8), echocardiography will be performed at pEOT visit and will not be required at Visit 8.
- (5) A chest X-ray that has been performed within 6 months prior to Screening can be used (in this case, there is no need to repeat the chest X-ray at Screening).
- (6) At each pre-dose assessment, SBP/DBP measurements will be performed twice in the supine position.
- (7) On Day 1 and at Re-initiation visit, SBP/DBP assessment and 12-lead ECG will be done pre-dose and hourly until 6 h post-dose; after 6 h, subjects may be discharged if they meet the discharge criteria, otherwise SBP/DBP assessments and 12-lead ECG will be performed hourly until discharge criteria are met. If discharge criteria are not met after 12 h, the subject must be permanently discontinued. At all other visits, only pre-dose SBP/DBP assessments and 12-lead ECG will be performed.

- (8) On Day 1 and at Re-initiation visit, 24-hour ECG Holter should start before dosing. The subject must return to the site on Day 2 (Visit 2a) / Re-initiation (Visit I2) for removal of the device after 24-hour recording.
- (9) On Day 1 and at Re-initiation visit, PK samples will be collected 6 hours after dosing. At Visits 3, 4, 5, and 8, PK samples will be collected pre-dose. At pEOT visit, in the event of premature treatment discontinuation during TP1 (i.e., before Visit 8) and at EOS visit, PK samples will be collected at any time during the visit and will not be required at Visit 8.
- (10) Hematology assessments, including coagulation tests will be performed at each visit until EOS, except FU2, FU3 and FU3a, and FU3b visits.
- (11) Serum pregnancy tests will be performed at Screening and EOS. Urine pregnancy tests will be performed at all other visits. To ensure compliance, the study personnel must remind WOCBP at each visit to use the methods of contraception defined for this study from the Screening visit until 6 months after taking the last dose of study treatment.
- (12) All AEs and SAEs occurring after signing the ICF and up to 6 months after study treatment discontinuation must be reported.
- (13) Sample for SLE biomarkers analyses will include: SLE biomarkers serum sample, serum EDTA sample and PAXgene sample.
- (14) If the subject discontinues study treatment prematurely, the pEOT visit should preferably take place no later than 7 days after last study drug intake. Subjects who prematurely discontinue treatment will remain in the study and continue to perform all assessments as per planned visit schedule. See Section 5.1.7 for additional details on premature discontinuation of study treatment.
- (15) Unscheduled visits may be performed at any time during the course of the study. Recording the changes in concomitant medications and in background SLE therapies since the last visit needs to be performed at each unscheduled visit. Further assessment including body weight, chest X-ray, 12-lead ECG, SBP/DBP, echocardiography, SLEDAI-2K, PGA, BILAG, FACIT-Fatigue Scale, PGIS-F, PGIC-F, SF-36v2™, Lupus QoL, laboratory assessments and other disease activity assessments may be performed at the discretion of the investigator.
- (16) Applicable for subjects having completed TP2 according to the protocol schedule up to Month 12 / EOT (Visit 14).

AE = adverse event; ALT = alanine aminotransferase; ANA = anti-nuclear antibodies; anti-dsDNA = anti-double-stranded deoxyribonucleic acid; anti-HAV = anti-hepatitis A virus; anti-HCV = anti-hepatitis C virus; anti-HEV = anti-hepatitis E virus; AST = aspartate aminotransferase; BILAG = British Isles Lupus Assessment Group; DBP = diastolic blood pressure; ECG = electrocardiogram; EDTA = ethylenediaminetetraacetic acid; EOS = End-of-Study; EOT = End-of-Treatment; FACIT-Fatigue = Functional Assessment of Chronic Illness Therapy-Fatigue Scale score; FU = follow-up; HEV-RNA PCR = hepatitis E virus ribonucleic acid polymerase chain reaction; HIV = human immunodeficiency virus; I = re-initiation; ICF = informed consent form; Ig = immunoglobulin; mSLEDAI-2k = modified Systemic Lupus Erythematosus Disease Activity Index-2000; NA = not applicable; OCT = optical coherence tomography; pEOT = premature discontinuation of study treatment or premature End-of-Treatment; PFT = pulmonary function test; PGA = Physician's Global Assessment; PGIC-F = Patient Global Impression of Change – Fatigue; PGIS-F = Patient Global Impression of Severity – Fatigue; PK = pharmacokinetic(s); QoL = Quality of life; SAE = serious adverse event; SBP = systolic blood pressure; SF-36v2™ = 36-Item Short Form Health Survey version 2; SFI = SLE Flare Index; SLE = systemic lupus erythematosus; SLEDAI-2K = Systemic Lupus Erythematosus Disease Activity Index-2000; TB = tuberculosis; TBIL = total bilirubin; U = unscheduled; WOCBP = women of childbearing potential.

12.2 Definitions of AEs of special interest

The definitions for AESIs are based on a systematic approach using SMQs. The additional relevant term can be added to the search or deleted appropriately providing the rationale for the change. The current proposal is based on MedDRA version 25.0. The following safety areas are addressed by the pre-defined AESIs. Note that all SMQs are considered as broad searches (i.e., including broad and narrow terms) unless noted otherwise.

Narratives will be written for all SAEs, pregnancy and death events reported to Global Drug Safety, including those not meeting the definition of AESIs.

- **Effect on HR and rhythm AESI**

Effect on HR and rhythm AESI are identified by the PTs in the following SMQ: **Bradyarrhythmias (incl conduction defects and disorders of sinus node function) (SMQ)**. Note that this SMQ only has narrow scope defined.

In addition, to the PTs included in Bradyarrhythmias (including conduction defects and disorders of sinus node function [SMQ]), the following PTs will be added to the search for AEs addressing effects on HR and rhythm:

“BRADYCARDIA”, “ELECTROCARDIOGRAM RR INTERVAL PROLONGED”, “HEART RATE DECREASED”, “CHRONOTROPIC INCOMPETENCE”, “PRESYNCOPE”, “SYNCOPE”, “LOSS OF CONSCIOUSNESS”, and “CENTRAL BRADYCARDIA”.

AESI Narratives will be written for AEs of confirmed symptomatic events on HR and rhythm (e.g., symptomatic bradycardia, etc.). Narratives will be written for AV block 2nd and 3rd degree, but not for AV block 1st degree.

- **Hypotension AESI**

The following PTs will be added to the search for AEs addressing hypotension: “BLOOD PRESSURE DECREASED”, “BLOOD PRESSURE DIASTOLIC DECREASED”, “BLOOD PRESSURE ORTHOSTATIC DECREASED”, “BLOOD PRESSURE SYSTOLIC DECREASED”, “DIASTOLIC HYPOTENSION”, “MEAN ARTERIAL PRESSURE DECREASED”, “ORTHOSTATIC HYPOTENSION”, “PROCEDURAL HYPOTENSION”, “HYPOTENSION”, “CIRCULATORY COLLAPSE”, “BLOOD PRESSURE AMBULATORY DECREASED”, “BLOOD PRESSURE IMMEASURABLE”, “BLOOD PRESSURE SYSTOLIC INSPIRATORY DECREASED”, “CT HYPOTENSION COMPLEX”, “DISTRIBUTIVE SHOCK”, “PROCEDURAL SHOCK”, “SHOCK”, “SHOCK HAEMORRHAGIC”, and “SHOCK SYMPTOM”, “HYPOTENSIVE CRISIS”, “POST PROCEDURAL HYPOTENSION”, “HYPOVOLAEMIC SHOCK”, “CARDIOGENIC SHOCK”, “PERIPHERAL CIRCULATORY FAILURE”.

AESI Narratives will be written for confirmed symptomatic hypotension events.

- **Cardiovascular AESI**

Cardiovascular AESI are identified by any PT in the following SMQs: **Ischaemic heart disease (SMQ, narrow scope)** or **Torsade de pointes/QT prolongation (SMQ, broad scope)** or **Cardiac failure (SMQ, narrow scope)**.

AESI Narratives will be written for these AESIs only if reported as SAE.

- **Hypertension AESI**

Hypertension AESIs are identified by the PTs in the following SMQ: **Hypertension (SMQ, narrow scope)**.

AESI Narratives will be written for these AESIs only if reported as SAE.

- **Hepatobiliary disorders / Liver enzyme abnormality AESI**

Hepatobiliary disorders/ Liver enzyme abnormality AESIs are identified by the PTs in the following SMQ: **Drug related hepatic disorders - comprehensive search (SMQ)**.

AESI Narratives will be written for lab abnormalities or AEs of ALT or AST $\geq 3 \times$ ULN. No narrative will be written for AEs declared without ALT or AST being $\geq 3 \times$ ULN.

- **Pulmonary AESI**

These AEs are identified by the PTs in the following SMQs: **Asthma/bronchospasm (SMQ)** or **Interstitial lung disease (SMQ)**.

The PTs “DYSPNOEA AT REST”, “DYSPNOEA” and “DYSPNOEA EXERTIONAL” which are not included in the above-mentioned SMQs are added to the search.

SMQs related to respiratory system do not cover all the PTs on investigation (i.e., AEs based on pulmonary function test or chest X-ray or computerized tomography scan). Therefore, the PT from the MedDRA SOC ‘Investigations’ identified by the following HLGT are added to the search: **‘Respiratory and pulmonary investigations (excl blood gases)’ (HLGT)** with the exception of the following PTs: “CAPNOGRAM NORMAL”, “END-TIDAL CO2 NORMAL”, “EXPIRATORY RESERVE VOLUME NORMAL”, “FORCED EXPIRATORY VOLUME NORMAL”, “FORCED VITAL CAPACITY NORMAL”, “FUNCTIONAL RESIDUAL CAPACITY NORMAL”, “INSPIRATORY CAPACITY NORMAL”, “MAXIMAL VOLUNTARY VENTILATION NORMAL”, “PEAK EXPIRATORY FLOW RATE NORMAL”, “PULMONARY FUNCTION CHALLENGE TEST NORMAL”, “PULMONARY FUNCTION TEST NORMAL”, “RHINOMANOMETRY NORMAL”, “SPIROMETRY NORMAL”, “TOTAL LUNG CAPACITY NORMAL”, “VITAL CAPACITY NORMAL”.

AESI Narratives will be written for Pulmonary Functional Tests meeting the study treatment discontinuation criteria defined in protocol section 5.1.8.3.

- **Macular edema AESI**

Macular edema AESI are identified by the following PTs: “MACULAR OEDEMA”, “MACULAR HOLE”, “MACULAR PSEUDOHOLE”, “MACULAR RUPTURE”, “MACULAR THICKENING”, “MACULAR CYST”, “RETINAL OEDEMA”, “DIABETIC RETINAL OEDEMA”, “CYSTOID MACULAR OEDEMA”, “PAPILLOEDEMA”, and “PSEUDOPAPILLOEDEMA”.

AESI Narratives will be written for cases reviewed by the Ophthalmology Safety Board.

- **Eye disorder AESI**

Eye disorder AESI are identified by the PTs in the following SMQ: **Retinal disorders (SMQ, narrow scope)**.

AESI Narratives will be written for cases reviewed by the Ophthalmology Safety Board.

- **Infection AESI**

Infection AESI are identified by the PTs in the following SMQ: **Opportunistic infection (SMQ)**.

AESI Narratives will be written for all these AESIs, except for COVID-19 cases that are not reported as SAE.

- **Skin malignancy AESI**

Skin malignancy AESI are identified by the PTs in the following SMQs: **Skin neoplasms, malignant and unspecified (SMQ)** or **Skin premalignant disorders (SMQ) (broad and narrow scope, including all sub SMQs)**.

[figure not shown]
AESI Narratives will be written for all these AESIs.

[figure not shown]
- **Non-skin malignancy AESI**

Non-skin malignancy AESI are identified by the PTs in the following SMQs: **Malignant tumours (SMQ)** or **Malignant lymphomas (SMQ; Narrow scope)** excluding the PTs included in the ‘Skin malignancy AESI’.

[figure not shown]
AESI Narratives will be written for all these AESIs.

